9.4.2. Electrocardiograms

Not applicable.

9.4.3. Vital Signs

For each patient, height and weight should be conducted according to the Schedule of Activities (Section 2).

9.4.4. Clinical Laboratory Tests

For each patient, HbA1c and FBG should be obtained locally according to the Schedule of Activities (Section 2).

Two-point FSBG [pre-breakfast (fasting) and post-breakfast (approximately 2 hours after breakfast)] should be measured on one day within 1 to 2 weeks before or at Visit 1 (Week 0), Visit 4 (Week 24), Visit 6 (Week 48), or the ET visit (if possible).

For each woman of childbearing potential (as assessed by the HCP), a urine pregnancy test should be obtained locally according to the Schedule of Activities (Section 2).

9.4.5. Other Tests

Not applicable.

9.4.6. Safety Monitoring

Lilly will periodically review evolving aggregate safety data within the study by appropriate methods.

9.5. Pharmacokinetics

Not applicable.

9.6. Pharmacodynamics

Not applicable.

9.7. Pharmacogenomics

Not applicable.

9.8. Biomarkers

Not applicable.

9.9. Medical Resource Utilization and Health Economics**9.9.1. Insulin Treatment Pattern**

The insulin treatment patterns of interest during the 48-week period were defined as follows:

- **Discontinuation:** Defined as stopping insulin treatment for 30 days or more. Time to discontinuation will be calculated as the number of days from initiation of insulin to insulin discontinuation or censoring. Time to insulin discontinuation and proportion of patient discontinued insulin will be compared.
- **Switch:** Defined as stop the initial insulin therapy and started another insulin therapy of different class. Proportion of patient switching and time to switching will be compared.

Note: Switching to a different brand of the same class will not be considered as an insulin treatment pattern switch.

- **Intensification:** Defined as any of the following: adding meal time insulin in basal insulin analog QD group; changing from BID to TID in insulin analog mid mixture BID group. Time to insulin treatment intensification and proportion of patient undergone insulin treatment intensification will be compared.
- **Reduction in frequency:** Defined as any of the following: changing from BID to QD; changing from TID to BID or QD. Time to insulin treatment reduction in frequency and proportion of patient undergone insulin treatment reduction in frequency will be compared.
- **Time to insulin treatment change:** Defined as time to any of: insulin treatment discontinuation, switch, intensification, or reduction in frequency.

Insulin treatment change and reason for insulin treatment change will be collected in the CRF by investigator and study-site personnel for all participants throughout the study.

9.9.2. Patient-Reported Outcomes

The self-reported questionnaires will be administered according to the Schedule of Activities (Section 2). These questionnaires have been translated into Chinese and linguistically validated.

Self-efficacy about Insulin Therapy Questionnaire (SEITQ). The SEITQ is designed to measure an individual's self-efficacy related to insulin therapy. The SEITQ consists of 5 items (that is, statements). The first 4 statements imply confidence in completing the tasks needed to take insulin correctly and avoid both hyperglycemia and hypoglycemia, whereas the last statement is an outcome expectation and implies that performance of these tasks will lead to avoidance of complications. The items are preceded by the stem "I am confident that I will be able to..." The directions ask respondents to indicate their level of agreement with each statement on a 7-point scale ranging from "1" (Strongly disagree) to "7" (Strongly Agree). The directions do not include a recall period nor do they refer to a specific insulin therapy or delivery system.

Insulin Treatment Satisfaction Questionnaire (ITSQ). The ITSQ is a validated measure consisting of 22 items that comprehensively assess treatment satisfaction for persons with

diabetes taking insulin. Items are measured on a 7-point scale, where lower scores reflect better outcomes. In addition to an overall score, the items that make up the 5 domains of satisfaction are categorized as: Inconvenience of Regimen (5 items), Lifestyle Flexibility (3 items), Glycemic Control (3 items), Hypoglycemic Control (5 items), and Insulin Delivery Device (6 items).

9.9.3. Healthcare Resource Utilization

Medical resource utilization data, associated with medical encounters, will be collected in the CRF by the investigator and study-site personnel for all participants throughout the study. Protocol-mandated procedures, tests, and encounters are excluded.

Healthcare resource utilization will be examined as all-cause and T2DM-related, and categorized as inpatient, outpatient, and ER utilizations:

- Inpatient hospital utilization will be identified using medical encounters where the place of service is an inpatient hospital facility.
- Outpatient utilization will be identified using medical encounters where the place of service is outpatient facility.
- Emergency room utilization will be identified using medical encounters where the place of service is an ER. Emergency room claims that have the same service date as a hospitalization will not be counted as an ER visit. Emergency room visits adjacent to a hospitalization will be considered a hospitalization and will not be counted as an ER visit.

The data collected may be used to conduct exploratory economic analyses and will include:

- number and duration of medical care encounters, including surgeries, and other selected procedures (inpatient and outpatient)
- reason and duration of hospitalization (total days length of stay, including duration by wards; for example, intensive care unit)
- number and character of diagnostic and therapeutic tests and procedures

10. Statistical Considerations

10.1. Sample Size Determination

The primary objective of the study will be evaluated using the classification method as proposed by Qu and colleagues (2011). With no prior hypothesis specified, the study will be considered a success if a conclusion may be reached by the classification method. With a 1:1 randomization ratio between insulin analog mid mixture BID and basal insulin analog QD, and assuming a non-inferiority margin of 0.4%, no treatment difference between mid mixture BID and basal insulin analog QD, and a common SD of 1.5% for the change from baseline in HbA1c at Week 24, 332 evaluable patients per arm will provide greater than 99% possibility for the study to reach a conclusion for primary analyses with 2-sided alpha level of 0.05. If we assume 20% of the patients will drop out without providing an evaluable post-baseline HbA1c), 415 patients per arm need to be randomized.

10.2. Populations for Analyses

For purposes of analysis, the following populations are defined:

Population	Description
Enrolled	All participants who signed informed consent.
Randomized	All participants who were enrolled and who were randomized to any one of the treatment groups.

10.3. Statistical Analyses

10.3.1. General Statistical Considerations

Statistical analysis of this study will be the responsibility of Lilly or its designee. Any change to the data analysis methods described in the protocol will require an amendment only if it changes a principal feature of the protocol. Any other change to the data analysis methods described in the protocol, and the justification for making the change, will be described in the statistical analysis plan (SAP) or the clinical study report (CSR). Additional exploratory analyses of data will be conducted, as deemed appropriate.

Given the nature of this pragmatic study, both efficacy and safety analyses will be performed on randomized patients. As sensitivity analyses, certain efficacy analyses may be repeated by censoring all efficacy data after patients changed the randomized treatment regimen.

All tests of treatment effects will be conducted at a 2-sided alpha level of 0.05, unless otherwise stated.

The baseline value for measurements will be defined as the last non-missing observation on or before the randomization visit. If no data are available, the baseline value will be treated as missing. The Week 24 value for measurements will be the last non-missing post-baseline observation up to 24 weeks, and the Week 48 value for measurements will be the last non-missing post-baseline observation up to 48 weeks.

For continuous measures, summary statistics will include at least the number of patients with data, mean, SD, median, minimum, and maximum. For categorical measures, summary statistics will include at least the number of patients with data, frequency counts, and percentages. For comparisons based on analysis models, the differences will be reported using LS means, along with 95% CIs and p-value. Sometimes, comparison on the summary statistics may be performed and p-values be provided, and such p-values should be viewed as a descriptive measure only. Unless specified otherwise, a two-sample t-test will be used for continuous measurements and Fisher's exact test will be used for categorical measurements.

10.3.2. Treatment Group Comparability

10.3.2.1. Patient Disposition

The overall study disposition status will be summarized over all enrolled patients. Reasons for screen failures and study discontinuations will be tabulated for each treatment arm and overall population.

10.3.2.2. Patient Characteristics

Patient characteristics at baseline (for example, demographics, diabetes history, and comorbidity) will be summarized by treatment arm and overall population. No formal statistical comparisons will be performed.

10.3.2.3. Concomitant Therapy

Anti-hyperglycemic concomitant therapy will be summarized at baseline and throughout the study by treatment arm and overall population. General concomitant therapy will not be collected or summarized.

10.3.2.4. Treatment Compliance

No patient-reported and HCP-perceived compliance of the treatment will be collected and summarized.

10.3.3. Efficacy Analyses

10.3.3.1. Primary Analyses

The primary outcome of the study is the change from baseline in HbA1c at Week 24. In this study, HbA1c will be only measured once post-baseline at Week 24, so missing measurements will not be imputed. In addition to common summary statistics for the change from baseline data, the comparison between 2 treatment arms will be conducted using an analysis of covariate (ANCOVA) model, with change from baseline in HbA1c as response, treatment as fixed effect and baseline HbA1c as a covariate. The 95% CI of LS means difference (insulin analog mid mixture BID – basal insulin analog QD) will be used to make conclusions for the comparison. Specifically, let L and U be the lower and upper limit of this CI. Then,

- If $L > -0.4\%$, the Non-inferiority (NI) of basal insulin analog QD to insulin analog mid mixture BID is established;
- If $L > 0\%$, the superiority of basal insulin analog QD to insulin analog mid mixture BID is established;

- If $U < 0.4\%$, the NI of insulin analog mid mixture BID to basal insulin analog QD is established;
- If $U < 0\%$, the superiority of insulin analog mid mixture BID to basal insulin analog QD is established;

For more details, refer to the SAP and Qu and colleagues (2011). P-value for the treatment contrast from the ANCOVA may still be displayed, but should not be used to make a conclusion.

As a sensitivity analyses, the primary analyses will be repeated by censoring all efficacy data after patients changed the randomized treatment regimen.

10.3.3.2. Secondary Analyses

For change from baseline in HbA1c at Week 48, the analyses model will be similar to the primary analyses model, and the sensitivity analyses will also be performed. Also, a mixed-model repeated measures (MMRM) model will be employed to analyze the HbA1c change from baseline at Week 48. This MMRM model will have all post-baseline HbA1c as responses, baseline HbA1c as a continuous covariate, treatment group, Visit (Week 24 or Visit 48), and treatment by visit interaction as fixed effects and patient as a random effect. Treatment contrast at Week 48 will be used for making the inference.

For change from baseline in venous FPG, FSBG-based FBG, PPG, BG excursion and bodyweight at Week 24 and Week 48, the analyses will be done similarly to the primary analyses model (ANCOVA for Week 24 and Week 48, and MMRM for Week 48), except for the comparison will be based on the treatment contrast p-value from the corresponding analyses model.

For percentages of patients reaching treatment goals ($<7\%$) at Week 24 and Week 48, no missing data will be imputed. Count and percentages of patients reaching treatment goals will be summarized (when calculating percentages, the denominator will be the patients with non-missing HbA1c data at Week 24 or Week 48), and also be analyzed by a logistic regression model, with logit link function, treatment as fixed effect and baseline HbA1c as continuous covariate. Same analyses strategy will be used for the composite endpoint of patients reaching treatment goals ($<7\%$) and did not switch from or discontinue study treatment, and did not take rescue medication.

Insulin dose at each visit will be descriptively summarized by treatment groups by total daily dose (IU and IU/kg).

Time to insulin treatment change (as defined in Section 9.9.1) will be compared between treatment arms by a log rank test at Week 48. Patients who did not have any insulin treatment change up to Week 48 (or up to early discontinuation) will be considered as censored at Week 48 (or time of early discontinuation) with no event.

10.3.4. Safety Analyses

General AEs will be collected in this study. Count and frequency of AEs will be summarized for overall study population and by treatment arm. Also, AEs as a cause for insulin treatment change will be collected, and summarized by treatment arm.

Serious adverse events will be collected and reported per Lilly standard operating procedure (SOP) and local regulatory requirement. Count and frequency of SAEs will be summarized by treatment arm.

The incidence rate of CRF-collected severe, nocturnal and total hypoglycemic events will be summarized by visit and for the overall study duration. Comparison between treatment arms will be performed by Fisher's exact test. The overall yearly rates (events/patient/year) of those hypoglycemic events, calculated as, for each patient, the number of episodes times 365.25 and then divided by the patient's treatment duration, will be summarized, and analyzed by a Negative-binomial regression model with treatment as fixed effects and log of (patient's treatment duration/365.25) as an offset variable.

10.3.5. Pharmacokinetic/Pharmacodynamic Analyses

No pharmacokinetic/pharmacodynamics (PK/PD) analyses will be performed in this study.

10.3.6. Other Analyses

10.3.6.1. Medical Resource Utilization and Health Economics

10.3.6.1.1. Adherence and Insulin Treatment Pattern

For these measurements, summary statistics will be provided, and comparison will be performed by appropriate general test (see Section 10.3.1).

10.3.6.1.2. Resource Utilization

Utilization data will be summarized descriptively by category across arms (for example, surgery, and hospitalization days) for a treatment arm, including a frequency table with tabular statistics. Tests for differences in proportions between treatment arms will be performed.

10.3.6.1.3. Insulin Treatment Satisfaction Questionnaire (ITSQ)

Overall and domain scores will be summarized and tabulated for ITSQ score at endpoint.

10.3.6.1.4. SEITQ = Self-efficacy about Insulin Therapy Questionnaire (SEITQ)

Categorical responses for the each question will be summarized at baseline and endpoint. Comparisons will also be performed.

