8.3.4. SEITQ = Self-efficacy about Insulin Therapy Questionnaire (SEITQ)

Categorical responses for the each question will be summarized at baseline and endpoint (24 weeks). The change in SEITQ score from baseline at 24 weeks for each treatment group will be presented and P-value will be show in tables. The descriptive statistics (n, mean, median,

standard deviation, minimum, and maximum) and P-value of a two-sample t-test will be reported also.

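### The planned comparisons of single SEITQ items have no named test and fall to Fisher's exact test, which ignores the order of the 7-point scale

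*Protocol*

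**What the plan says.** - **The scale.** Protocol 9.9.2 describes five SEITQ items, for each of which the patient gives a "level of agreement with each statement on a 7-point scale", from 1 (strong disagreement) to 7 (strong agreement). Four items concern confidence in tasks; the fifth is an outcome expectation.
- **The Protocol's item analysis.** Section 10.3.6.1.4 reads in full: "Categorical responses for the each question will be summarized at baseline and endpoint. Comparisons will also be performed". It names neither the test nor the week.
- **The default.** Protocol 10.3.1, repeated in SAP 8: "Unless specified otherwise, a two-sample t-test will be used for continuous measurements and Fisher's exact test will be used for categorical measurements".
- **The link to the default.** The Protocol synopsis leaves patient-reported outcomes to a suitable general test. Protocol 10.3.6.1.1 uses the same phrase for treatment-pattern data and points to 10.3.1. SAP 8.3.1 resolves it, for those data, to Fisher's exact test.
- **The SAP's SEITQ section.** SAP 8.3.4 starts from the same sentence and dates it: "Categorical responses for the each question will be summarized at baseline and endpoint (24 weeks"). It then turns to the score: "The change in SEITQ score from baseline at 24 weeks for each treatment group will be presented and P-value will be show in tables". The only test it names is a two-sample t-test. The Protocol's sentence about comparisons is absent.
- **The endpoints.** The objectives tables list the change in SEITQ score at Week 48 (secondary) and at Week 24 (exploratory). Neither is an item-level endpoint.

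**The concern.** Fisher's exact test on a 2 x 7 table asks whether the two response patterns differ in any way. It gives the same p-value if the seven columns are shuffled. A treatment that moves patients up or down an agreement scale has an effect in one direction. An unordered test spreads its sensitivity over 6 degrees of freedom to look for that effect, where a rank or ordinal test uses one. It also makes no use of the baseline response to the same item, which is collected at Visit 1.

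What is at stake is modest. The items cover different things, so item comparisons could help to explain a difference in the score. Under the default they could miss a real shift, or give a small p-value that does not speak to direction; the reader would have to take direction from the tables.

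**Working it through.** **1. Inputs from the documents.** Two-sided alpha 0.05 (Protocol 10.3.1). Five items with seven ordered levels (Protocol 9.9.2). 332 evaluable patients per arm (Protocol 10.1, SAP 5), chosen for HbA1c with SD 1.5% and margin 0.4%. No SEITQ distribution, effect size, power or completion rate is given.

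**2. The plan's own figures.** SE = 1.5 x sqrt(2/332) = 0.1164. The 95% CI half-width is 1.96 x 0.1164 = 0.228, below 0.4, so at that SD at least one non-inferiority statement is always reached. This agrees with the stated probability above 99%. With 20% dropout, 332/0.80 = 415 per arm. These reproduce, but they say nothing about SEITQ.

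**3. Large-sample comparison.** Take a shift that gives the same noncentrality in a 1-df ordinal test (critical value 3.84) and in the 6-df test of the 2 x 7 table (critical value 12.59).

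| Ordinal test, 1 df | Unordered test, 6 df | Loss (points) |
|---|---|---|
| 8% | 6% | 2 |
| 20% | 11% | 9 |
| 30% | 15% | 15 |
| 40% | 20% | 20 |
| 50% | 26% | 24 |
| 70% | 41% | 29 |
| 80% | 52% | 28 |
| 90% | 67% | 23 |
| 95% | 78% | 17 |
| 99% | 92% | 7 |
| 99.9% | 98% | 2 |

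**4. Fisher's exact test itself.** Monte Carlo version for a 2 x 7 table against the Wilcoxon test, 332 per arm, proportional-odds shift, 1,500 runs per setting. Assumed distributions over levels 1 to 7: central (3, 7, 15, 25, 25, 15, 10%) and skewed high (1, 2, 4, 10, 20, 35, 28%).

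| Distribution | Odds ratio | Fisher | Wilcoxon | Loss (points) |
|---|---|---|---|---|
| Central | 1.3 | 24% | 50% | 26 |
| Central | 1.4 | 39% | 68% | 29 |
| Central | 1.5 | 58% | 85% | 27 |
| Skewed high | 1.3 | 25% | 46% | 21 |
| Skewed high | 1.4 | 40% | 68% | 28 |
| Skewed high | 1.5 | 54% | 82% | 28 |

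With no difference (central distribution) the rejection rates are 4.9% and 4.7%, so neither test gains from an inflated error rate. The Pearson chi-square, a close stand-in here, was run over four distributions and odds ratios 1.2 to 1.75. It gave losses of 10 to 30 points.

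**5. A wider range of shifts.** Assumed distribution 2, 4, 8, 16, 25, 27, 18%, shift on a latent normal scale, chi-square against Wilcoxon, 20,000 runs each.

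| Shift (SD) | Unordered | Rank | Loss (points) |
|---|---|---|---|
| 0.05 | 6% | 9% | 3 |
| 0.10 | 12% | 23% | 11 |
| 0.15 | 23% | 45% | 23 |
| 0.20 | 41% | 69% | 28 |
| 0.25 | 61% | 86% | 25 |
| 0.30 | 80% | 95% | 16 |
| 0.35 | 92% | 99% | 7 |
| 0.40 | 97% | 99.8% | 2 |

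**6. Where the claim stops.** If the second arm instead spreads to both ends (4, 6, 8, 13, 20, 26, 23% against the distribution in step 5), the unordered test has 56% power and the Wilcoxon test 8%. The advantage of the rank test depends on a consistent shift.

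**The case against.** The strongest reply is that the item comparison may no longer exist. Protocol 10.3.1 lets the SAP change analysis methods. SAP 8.3.4 keeps the item summary, omits the sentence about comparisons, and tests the score by a t-test, which uses the order of the scale. Elsewhere among the exploratory analyses (SAP 8.3.1, 8.3.2, 8.3.5) the SAP names Fisher's exact test where it wants it. On that reading the items are descriptive.

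This is a fair reading, but not the only one. Protocol 10.3.1 asks that a change of method and its justification be described in the SAP or the study report, and the SAP does not say that the item comparisons are dropped. The Protocol's commitment and the default in both documents therefore still stand.

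Three parts of the reply hold. Fisher's exact test is inferred from a default; no SEITQ section names it. Both documents say that p-values from comparisons of summary statistics are descriptive, which makes power a weaker criterion. And the unadjusted Wilcoxon test ignores the baseline response just as Fisher's does.

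A reader might infer that the secondary SEITQ endpoint is tested with a weak method. The documents do not support that: it is a change in score, a continuous measure for which the default is a t-test.

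**Conclusion.** The point holds in a limited form. The Protocol plans item-level SEITQ comparisons without a test, the default is one that ignores order, and the SAP does not settle whether they are kept. No primary, secondary or listed exploratory endpoint is affected.

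The size is conditional. Under assumed distributions, a consistent shift and 332 per arm, the loss is roughly 2 to 30 points, and about 20 to 30 points only when the rank test has about 40% to 90% power. A single figure for the loss would claim more than the documents allow, because they give no SEITQ effect or distribution and the sample size was set for HbA1c. For a non-monotone difference the unordered test can be the stronger one. This is a desirable improvement and changes no main conclusion.

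**What to change.** In SAP 8.3.4 and Protocol 10.3.6.1.4:

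- State that SEITQ item responses are exempt from the Fisher default.
- Compare each item between arms with a proportional-odds model containing treatment and the baseline item response, and report the odds ratio with its 95% CI. A Wilcoxon rank-sum test is a simpler, unadjusted alternative.
- Name the week or weeks, since the Protocol says only endpoint and the SAP says Week 24.
- Label these comparisons exploratory.

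If the sponsor meant the items to be descriptive only, the SAP should say so and the Protocol sentence should be aligned with it.

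The cost is a few sentences and a routine procedure, with no new data or patients. The small downside is the proportional-odds assumption, which the Wilcoxon alternative avoids. The t-test on the score needs no change for this point. Separately, SAP 8.3.4 covers only Week 24, and SAP 8.2.2 gives no analysis of the Week 48 score change beyond naming the score in its carry-forward rule; that can be settled in the same edit.
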